Appendix 9: Trial Conduct During National or International Public Health Emergency

It is recognized widely that the COVID-19 pandemic has impacted the conduct of clinical trials. The COVID-19 pandemic is still running and may again trouble the conduct of clinical trials in the coming months before any preventive treatment becomes available. The impact is unknown at this point. However, challenges may arise in the next months from COVID-19 or similar disease. It may cause for example, quarantines self-imposed or institute imposed or governmental imposed, site closures, travel limitations, interruptions in the supply chain for the study drugs, or other considerations if site personnel or trial subjects become infected with COVID-19. These challenges may lead to difficulties in meeting protocol-specified procedures including administering the study drug or adhering to protocol-mandated visits and laboratory/diagnostic testing.

The Sponsor is providing the following exceptional options for study related patient management in the event of disruption to the conduct of the study during the pandemic/epidemic time:

1. If scheduled visits cannot be conducted in person at the study site, it should be performed remotely/virtually or delayed until such time that on-site visits can be resumed. At each contact, patients should be interviewed to collect safety data. Patients will also be questioned regarding general health status to fulfill physical examination requirements.
2. Study drug administrations are allowed only at site according to the procedure described in the protocol. In case of any issue with study administration schedule investigator must contact the Sponsor as indicated in [Section 5.6.1](#).
3. Efficacy endpoint assessments should be performed if required and as feasible. If not, the sponsor should be contacted to advise the investigator on how to proceed.
4. Every effort should be made to adhere to protocol-specified assessments for patients on study intervention including follow-up. Safety laboratory assessment can be performed at the local laboratory near the patient, if possible.
5. In case of patient's withdrawal, if the withdrawal visit is done remotely, an on-site visit will be organized once the situation is stabilized.
6. Study sites should inform the Sponsor about modifications as soon as possible.
7. Missed assessment/visits should be captured as protocol deviations due to COVID-19.
8. Changes to study procedures should be documented in the source notes and in the e-CRF as advised by the Sponsor. Specific information for individual patients should be captured in the e-CRF that explains the basis for missing protocol-specified information in relationship to COVID-19, *i.e.*, from missed study visits or study discontinuations due to COVID-19.

I.R.I.S. as the Sponsor of the study will continue to monitor the conduct and progress of the clinical study during pandemic/epidemic scenario and any changes (*e.g.*, delay or discontinuation in recruitment, site monitoring and audits) will be communicated to the sites and to the Health Authorities according to local guidance. Modifications made to the study conduct as a result of disruption the COVID-19 pandemic/epidemic will be summarized in the Clinical Study Report. This guidance does not supersede any local or government requirements or the clinical judgement of the investigator to protect the health and well-being of patients and site staff.

e.g.	Exempli gratia (for example)
ERIN	Event Requiring Immediate Notification
ESSDAI	EULAR Sjögren's Syndrome Disease Activity Index
ESSPRI	EULAR Sjögren's Syndrome Patient Reported Index
ESR	Erythrocyte Sedimentation Rate
EULAR	European League against Rheumatism
FU	Follow-up (period)
GCP	Good Clinical Practice
ICF	Information Consent Form
ICH	International Conference on Harmonisation
i.e.	id est (that is)
IE	Intercurrent Event
IL-7	Interleukin 7
IL-7R α	Alpha chain of the Interleukin 7 (IL-7) Receptor (=CD127)
IMP	Investigational Medicinal Product (S95011/Placebo)
I.R.I.S.	Institut de Recherches Internationales Servier
IV	Intravenous
IWRS	Interactive Web Response System
kg	kilogram
L	Litre
LLN	Lower Limit of Normal laboratory reference range
LLOD	Lower Limit Of Detection
LLOQ	Lower Limit Of Quantification
LLS	Lower Limit used to define potentially clinically Significant abnormal values
MAR	Missing At Random

CL2-95011-001 - Statistical Analysis Plan | VV-TMF-116033 | 2.0

MFI	Multidimensional Fatigue Inventory
mg	milligram
min	minute
mL	Millilitre
mm	Millimetre
mmHG	Millimetre of mercury
MNAR	Missing Not At Random
NRS	Numerical Rating Scale
NSAID	Non-steroidal anti-inflammatory drugs
OSS	Ocular Staining Score
PBMCs	Peripheral Blood Mononuclear Cells
PD	Pharmacodynamics
PK	Pharmacokinetics
PGA	Patient's global assessment
PhGA	Physician's global assessment
PSS	Primary Sjögren's Syndrome
QoL	Quality Of Life
RF	Rheumatoid Factor
RNA	RiboNucleic Acid
RO	Receptor Occupancy
RS	Randomised Set
SAE	Serious Adverse Event
SAP	Statistical Analysis Plan
SBP	Systolic Blood Pressure
SF-36	Short Form Health Survey
SSA	Sjögren's syndrome A
STAR	Sjogren's Tool for Assessing Response
TEAE	Treatment Emergent Adverse Event
TLG	Tables Listings and Graphs
TU	Therapeutic Units
ULN	Upper Limit of Normal laboratory reference range
ULS	Upper Limit used to define potentially clinically Significant abnormal values
ULOD	Upper Limit Of Detection
W	Week
WHO	World Health Organization

1. INTRODUCTION

This Statistical Analysis Plan deals with the main analysis of the study (ASSE-W013 period) and the follow-up period (ASSE-W028) and details the planned analyses to be performed, in accordance with the main characteristics of the amended study protocol version 4.0 dated from 24/03/2022.

The templates for Tables, Listings and Graphs (TLG) are described in a separate document.

The main analysis of the study concerns the ASSE-W013 period and will be performed as soon as all efficacy and safety data of the ASSE-W013 period are available and the mandatory steps required for study unblinding have been performed. The descriptive analysis including data after W013 will be performed subsequently when all data are available.

Of note, this SAP does not cover analyses of data associated to some exploratory objectives and the pharmacokinetics and pharmacodynamics data analyses described in the study protocol.

1.1. Study objectives and endpoints

1.1.1. Objectives

The purpose of this trial is to assess the efficacy and safety of multiple intravenous infusions of 750 mg of S95011 versus placebo as well as tolerability, pharmacokinetics and pharmacodynamics in patients with primary Sjögren's syndrome (pSS). The results of this first study in patients with primary Sjögren's syndrome will be informative for further development in treatment of pSS.

The primary objective of the study is to assess the effect of multiple intravenous infusions of 750 mg of S95011 compared to placebo after 13 weeks of treatment in reducing disease activity using European League against Rheumatism (EULAR) Sjögren Syndrome Disease Activity Index (ESSDAI).

The secondary objectives are:

- To evaluate efficacy of multiple intravenous (IV) infusions of 750 mg of S95011 compared to placebo after 13 weeks of treatment on:
 - Patient's symptoms using EULAR Sjögren Syndrome patient reported Index (ESSPRI).
 - Disease activity using Sjogren's Tool for Assessing Response (STAR).
 - Disease activity using Composite of Relevant Endpoints for Sjögren's Syndrome (CRESS).
 - Fatigue using the Multidimensional Fatigue Inventory (MFI).
 - Quality of life (QoL) using Short Form Health Survey (SF-36).
 - Physician's global assessment (PhGA) of the disease activity using a 0 to 10 numerical rating scale (NRS).
 - Patient's global assessment (PGA) of the disease activity using a 0 to 10 numerical rating scale (NRS).
 - Tear gland function using the Schirmer test.
 - Tear gland function using Ocular Staining Score (OSS).
 - Salivary gland function measured by sialometry under unstimulated and stimulated conditions.
- To assess the safety and tolerability of multiple intravenous infusions of S95011.
- To assess the pharmacokinetics (PK) of S95011 in serum.
- To assess pharmacodynamics [receptor occupancy (RO)] of S95011 in blood.
- To determine the incidence of anti-drug antibodies (ADA) formation.

The exploratory objectives of the study are:

- To explore the potential effect of S95011 on lymphocytes subsets in particular T cell subsets.
- To explore the potential effect of S95011 on some proteins involved in pSS physiopathology like Interleukin 7 (IL-7), cytokines and specific proteins in blood.
- To explore the potential effect of S95011 on immune panel, β 2 microglobulin, and on the auto-antibody panel: Anti-Sjögren's Syndrome related antigen A (anti-SSA (Ro)) antibodies, anti-nuclear antibodies (ANA) and rheumatoid factor (RF).
- To explore drug exposure and perform exploratory histology and exploratory biomarkers assessments on minor salivary glands tissue by performing lip biopsies (optional).
- To set a biocollection to explore further the potential impact of S95011 on Peripheral Blood Mononuclear Cells (PBMC), extracted Ribonucleic Acid (RNA) and blood according to the advancement of the knowledge on the drug and the disease (optional sampling) (not covered by the SAP).

1.1.2. Endpoints

The primary efficacy endpoint is the change from baseline in ESSDAI total score to W013.

The secondary efficacy endpoints are:

- ESSDAI score by domain and total score at each visit (value & change).
- ESSPRI score by symptom and total score at each visit (value & change).
- Proportion of patients with ≥ 3 points, ≥ 5 points, ≥ 7 points of improvement from baseline in ESSDAI at each visit.
- Proportion of patients with ≥ 1 point, ≥ 2 points, ≥ 3 points of improvement from baseline in ESSPRI at each visit.
- Proportion of patients with ≥ 3 points of improvement in ESSDAI and with ≥ 1 point of improvement in ESSPRI from baseline at each visit.
- Proportion of patients with a STAR total score ≥ 5 at each visit (value).
- Proportion of patients with a CRESS total score ≥ 3 at each visit (value).
- Fatigue (MFI) by domain, quality of life (SF-36) for mental and physical domains, physician and patient's global assessment of the disease activity (NRS) at each visit (value and change).
- Tear gland function: Schirmer's test and in OSS on the most affected eye and for the mean of both eyes at each visit (value and change).
- Salivary gland function: unstimulated and stimulated salivary flow rate at each visit (value and change).

The other secondary endpoints are:

- **Safety:** The safety and tolerability assessed by incidence of adverse events (AEs), change over time in safety parameters (vital signs, biological laboratory) and incidence of abnormal safety parameters throughout the study.
- **Pharmacokinetics:** Pharmacokinetics of S95011 in serum samples:
 - Pre-dose (before the start of the IMP infusion) at W000, W002, W004, W007, and W010.
 - Right after the end of the IMP infusion and in the [1-3h] interval after the end of the IMP infusion at W000 and W010.
 - Between W011 and W012, and at W013, W016, W019 and W028.

CL2-95011-001 - Statistical Analysis Plan | VV-TMF-116033 | 2.0

- **Pharmacodynamics:** Receptor Occupancy (RO) of S95011 in blood samples:
 - Pre-dose (before the start of the infusion) at W000, W002, W004, W007 and W010.
 - Right after the end of the infusion of the IMP at W000 and W010.
 - At W013, W019, W028.
- **Incidence of ADA** in serum samples:
 - Pre-dose (before the start of the infusion) at W000, W002, W004, W007 and W010.
 - At W013, W019, W028.

The exploratory endpoints are:

- **In blood:**
 - Lymphocytes subsets (PBMC) assessed at W000, W004, W007, W013.
 - IL-7 and some cytokines measured at W000, W002, W004, W007, W010, W013, W019, W028.
 - Other specific proteins involved in the pSS physiopathology will be measured at W000, W004, W013.
 - Cytokine release panel at W000 and W002.
 - Immune panel at ASSE (Selection visit), W000, W004, W013.
 - Auto antibody-panel at ASSE, W013.
 - β 2 microglobulin at W000, W004, W013.
- **In salivary glands:**
 - Lip biopsy for salivary gland collection (S95011 concentration, exploratory histology and exploratory biomarkers assessments) (optional biopsy at W013).

1.1.3. Study design

The study CL2-95011-001 is a phase IIa, international, multicentre, randomised (2:1), double-blind, placebo-controlled study with two parallel groups (S95011 750 mg and placebo).

1.1.4. Study plan

The study is divided into the following periods:

- **Screening period without study treatment:** from selection visit (ASSE within 28 days prior to W000) to inclusion visit (W000), after signing the ICF, in order to check eligibility of patients.
- **Randomised and double-blind treatment** period: from W000 to W013 (study drug administration at W000, W002, W004, W007, W010) with two-parallel groups (750 mg of S95011 and matching placebo), with stratification by baseline intake of oral corticosteroids (yes/no) and baseline intake of antimalarial (*e.g.* chloroquine, hydroxychloroquine, quinacrine) (yes/no).
- **Safety follow up period without study treatment:** 15 weeks with one visit at W019 and one at W028. This follow-up period will allow sufficient time for monitoring safety until 5 half-lives of S95011. In addition, it is anticipated that more than 97% of patients have RO < 95% at W028 (meaning that almost no pharmacological effect of the product is expected).

[figure not shown]
The expected duration of patient participation will be 32 weeks maximum.

Study treatments are supplied as follows:

- **During the screening period (from ASSE to W000)**, no treatment will be dispensed.
- **From the day after inclusion until the day of W013 visit**, patients take one (1) IV infusion of 750 mg of S95011 or matching placebo every two weeks (q2w) for the first month (W000, W002, W004) and then every 3 weeks (q3w) until W010 (W007, W010). S95011/matching placebo will be provided to the site in 2 mL extractable volume vials containing 100 mg of S95011/matching placebo (50 mg/mL) concentrate for solution for intravenous administration. As treatment is dispensed during a double-blind period, the appearance and form of S95011 vials and placebo vials as well as the solutions to be administered will be similar: a colourless to slightly yellow, clear to slightly opalescent aqueous solution.
- **From the day after W013 visit until the day of W028 visit**, follow-up period.

The study plan is shown in [Figure \(1.1.4\) 1](#).

Figure (1.1.4) 1 - Study plan

*One blood sample will be performed for PK assessment between W011 and W012 and at W16 (± 5 days), at site or not according to local facilities.

1.1.5. Type of randomization

The treatment randomization and allocation are centralized using an Interactive Web Response System (IWRS) procedure. The treatment (S95011 750 mg or placebo) is assigned at inclusion visit by a non-balanced 2:1 ratio, non-adaptive randomization with stratification by baseline intake of oral corticosteroids (yes/no) and baseline intake of antimalarials (*e.g.*: chloroquine, hydroxychloroquine, quinacrine) (yes/no).

1.2. Determination of sample size

The following efficacy criteria are defined:

- A statistically significant reduction in ESSDAI at W013 in the S95011 group compared to placebo, at the one-sided 10% significance level.
- An estimated mean reduction in ESSDAI in the S95011 group to be 3 points or greater than placebo. The decrease of 3 points was chosen because it is considered as clinically minimal relevant decrease ([Seror et al, 2016](#)).

Targeted sample size

With 45 patients in the primary analysis of the primary estimand (30 in the S95011 group and 15 in the placebo group), the study would have around 5% chance of having a false-positive result, *i.e.*, of meeting both the efficacy criteria when the true difference between S95011 and placebo is zero. Additionally, the chances of meeting both the efficacy criteria remain below 14% for true differences between S95011 and placebo of less than 1 point.

The study would have approximately 70% chance of meeting both the efficacy criteria, when the true difference between S95011 and placebo is 4 points. In case the true difference between S95011 and placebo is only 3 points, the study would have approximately 50% chance of meeting both the efficacy criteria. These calculations assume that the primary efficacy endpoint, change from baseline in ESSDAI, follows a normal distribution with a standard deviation of 6. This estimate of the standard deviation is based on some clinical studies (Fisher *et al*, 2020, UCB5857, RO5459072) in patients with primary Sjögren's syndrome in which the observed standard deviation ranged from around 4 to 6.

Blinded standard deviation reassessment

The similar operational characteristics (false-positive and right-positive rates) are obtained with 20 patients in S95011 group and 10 patients in placebo group under assumption of an overall standard deviation of primary efficacy endpoint of 5. So only if the recruitment is much longer than expected, when 30 patients will have completed the 13-week treatment period, the overall standard deviation of the primary endpoint on non-comparative data could be calculated. If the value is less or equal to 5, the sponsor could stop the patient recruitment, considering that the number of patients is sufficient to meet both efficacy criteria. This potential adaptation has very little or no impact on the probability of having a false-positive result (Kieser, 2003).

2. ANALYSIS SETS / TREATMENT GROUPS

2.1. Analysis sets

- **Randomised Set (RS):**
All included patients to whom a therapeutic unit (TU) was randomly assigned using IWRS.
- **Safety Set (SS):**
All patients having taken at least one dose of IMP.
- **Biomarker Set (BMKS):**
All patients of the RS having at least one available result for any biomarker.

2.2. Treatment groups

Treatment groups considered will be S95011 (750 mg) and placebo.

They will correspond to treatment received at inclusion visit.

In the unlikely event of a patient receiving an incorrect Therapeutic Unit (TU) at a particular post-W000 visit on the 13-week double-blind treatment period, which would result in a switch of treatment group, the patient will be considered in the treatment group corresponding to their TU(s) received until the switch. Their data recorded from the switch will be managed according to the considered estimand. All safety data and IMP administration data of the patients with a switch of treatment group will be listed separately.

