10.1.1.2. Treatment groups

Treatment groups considered will be S95011 and placebo.

They will correspond to randomised treatment except for safety analyses for which treatment taken at inclusion visit will be considered.

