10.1.2.4. Efficacy analysis

10.1.2.4.1. Primary estimand based on the ESSDAI

The primary estimand of interest is the effect of the initially randomised treatments on the clinical disease activity in all patients assuming non-occurrence of intercurrent events. The motivation for this choice is to assess at this proof-of-concept stage the full efficacy potential, that is, the pharmacologic effect of the S95011 if all patients adhere to it (without any intercurrent events).

The attributes of the primary estimand are defined as follow:

- Treatment: S95011 or placebo
- Population: RS
- Variable: change in ESSDAI total score from baseline to W13 (primary efficacy endpoint).
- Summary measure: difference in means between treatments.
- Intercurrent events (IE):
 - change or initiation of unauthorised medication
 - study drug discontinuation for major worsening of primary Sjögren's syndrome or AE related to study drug
 - study drug discontinuation for other reasons (non-medical reason, AE not-related...)
 - unexpected others events having a major impact on the pharmacologic effect evaluation (They will be defined at the latest in the final version of the SAP).

The rate of IEs is assumed to be below 10%. They will be handled by a hypothetical strategy to estimate what the outcome would have been at the designated time point if no IE would have occurred through that time point, considering that patients with IE would have efficacy outcomes as patients, in their treatment group, who continue their randomised treatment without IE.

10.1.2.4.1.1. Primary analysis

The primary analysis for the primary estimand will be conducted using only data obtained prior to IEs. Values post IE will not be taken into account and will be imputed according to the MAR assumption (multiple imputation by treatment group). This is aligned with the primary estimand and the hypothetical strategy.

S95011 will be compared to placebo on the primary efficacy endpoint in the RS, using a General Linear Model including the fixed, categorical effect of treatment and randomisation stratification factors (*rando_factor*) as well as the continuous fixed covariate of baseline value.

GENERAL LINEAR MODEL: change = baseline rando_factors treatment

The assumptions underlying the model, as for instance, the normality and homoscedasticity of residuals and detection of outliers, will be checked.

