4.3.3. Additional estimands based on ESSDAI and ESSPRI

Treatment policy estimands

Treatment policy estimands are defined in order to assess the treatment effect on the clinical disease activity (ESSDAI total score) and also on the symptoms reported by the patients (ESSPRI total score) regardless of whether or not the IE occurs.

The attributes of the additional estimands are defined as follow:

- Treatment: S95011 or placebo.
- Population: RS.
- Variable 1: change in ESSDAI total score from baseline to W013.
- Variable 2: change in ESSPRI total score from baseline to W013.
- Summary measure: difference in means between treatments.
- Intercurrent events: The occurrence of IEs (see list in primary estimand) is irrelevant in defining the treatment effect of interest. All observed values will be used regardless of occurrence of an IE.

Missing data not due to IE will be handled according to the MAR assumption as in the primary analysis.

Main analysis is the same as for the primary estimand. Supplementary analysis will be performed as for the primary estimand but considering the responders in ESSDAI at W013 defined as patients having improvement from baseline in ESSDAI total score of at least:

- 3 points

as well as on the responders in ESSPRI at W013 defined as patients having improvement from baseline in ESSPRI total score of at least:

- 1 point

using the same model as for responders ESSDAI for the primary estimand (Section 4.3.1.3).

Other estimand

This estimand of interest is the effect of the treatments on the composite response to treatment taking into account a double dimension - clinical disease activity from ESSDAI and symptoms reported by the patients from ESSPRI - in all patients assuming non-occurrence of IEs. The motivation for this choice is the same as the primary estimand.

The attributes of this estimand are defined as follows:

- Treatment: S95011 or placebo.
- Population: all randomised patients (RS).
- Variable: Number of responders defined as patients with ≥ 3 points of improvement in ESSDAI and with ≥ 1 point of improvement in ESSPRI from baseline at W013.
- Summary measure: difference in proportion between treatments.
- Intercurrent events (IE):
 - IE1: Study drug discontinuation for major worsening of primary Sjögren's syndrome.
 - IE2: Increase or initiation of authorized medication for pSS.
 - IE3: Study drug discontinuation for AE related to study drug.

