6. CHANGES TO PROTOCOL-PLANNED ANALYSES

The definition of the Randomised Set has been modified as the set of all included patients to whom a therapeutic unit (TU) was randomly assigned using IWRS. Indeed, a patient non included has been randomised by mistake. According to the ICH E9 addendum, the population has to be defined according to the clinical question of interest. So, it has been judged relevant to define the analysis population as above.

The definition of treatment groups has been modified as the treatment received at inclusion visit for all analysis sets. Indeed, a patient has been randomised to one treatment but received the other one at inclusion (forced allocation). Thus, this patient has continued taking treatment received instead of randomised treatment for the following dispensations and it has been judged relevant to define the treatment groups as above.

As a patient received an incorrect Therapeutic Unit (TU) at a post-W000 visit on the 13-week double-blind treatment period, this patient has potentially switched treatment group. Thus, it has been decided to complete the definition of treatment groups by precisizing that in such cases, the patient will be considered in the treatment group corresponding to their TU(s) received until the switch. The switch being considered as an intercurrent event, data recorded from the switch will be managed according to the considered estimand.

Since the final version of the protocol, a new score for assessment of Sjögren has been constructed. It has been considered relevant to add this new score (STAR) in the statistical analyses. Thus, a new objective and associated secondary analyses have been added in this SAP.

In the same line, the CRESS score (a score similar to STAR) has been considered relevant to evaluate the efficacy of S95011. Thus, a new objective and associated secondary analyses have been added in this SAP for this score.

As descriptive statistics has been considered sufficient to evaluate the efficacy of S95011 on the MFI, SF-36 and stimulated salivary flow, the estimands and associated inferential analyses has been deleted.

The BMK set has been added to the list of analysis sets in order to perform Biomarker exploratory analyses.

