Regarding the estimand framework, some changes has been made between the protocol and the SAP on intercurrent events. Indeed, “*study drug discontinuation for major worsening of primary Sjögren’s syndrome or AE related to study drug*” has been split into two independent IEs as “*study drug discontinuation for major worsening of primary Sjögren’s syndrome*” (IE1) is considered more impacting than “*Study drug discontinuation for AE related to study drug*” (IE3). Thus, for sensitivity analyses, it is has been decided to handle data post the IE1 using a reference based multiple imputation (“jump to placebo” approach) while data post the IE3 are considered moderately bad outcome and will be handled using a reference based multiple imputation (“copy increment in reference” approach). In the same line, intercurrent event “*change or initiation of unauthorised medication*” from the protocol has been split into “*Increase or initiation of authorized medication for pSS*”(IE2) and “*Decrease or stop of authorized medication for pSS*” (IE6) (the unauthorized part being necessarily linked to discontinuation for major worsening this part is already handled by IE1). Here again, IE2 having more impact than IE6, post IE data will be handled using different method (respectively reference based multiple imputation “copy increment in reference” and MAR approaches) for sensitivity analyses. Finally, IE5 “*Switch of treatment group (error of dispensation)*” has been added to handle the case of the patient having a treatment switch discussed above (MAR approach).

For all efficacy analyses, it has been specified that if the regression or the imputation model does not run due to too few patients in the stratas, the four classes randomisation stratification factor will be replaced by a 2 classes composite factor: baseline intake of oral corticosteroids or antimalarial or both (yes/no). If the model is still not running, then the stratification factor will not be considered.

Finally, for the treatment policy efficacy analysis, it has been considered sufficient to consider only responders in ESSDAI defined as patients with an improvement of at least 3 points and responders in ESSPRI defined as patients with an improvement of at least 1 point.

The salivary gland tissue will not be described because of the very small number of available biopsies collected at W013.

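### The ESSDAI and ESSPRI treatment-policy analyses group patients by treatment received at W000, so no planned efficacy analysis groups them as randomised

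*SAP*

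**What the plan says.** Protocol 10.1.1.2 separates efficacy from safety when it defines the groups: "They will correspond to randomised treatment except for safety analyses for which treatment taken at inclusion visit will be considered". Its primary estimand (10.1.2.4.1) is worded to match: "The primary estimand of interest is the effect of the initially randomised treatments on the clinical disease activity in all patients".

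SAP 2.2 replaces that rule with a single one: "They will correspond to treatment received at inclusion visit". SAP 6 gives the scope, "The definition of treatment groups has been modified as the treatment received at inclusion visit for all analysis sets", and the reason, "Indeed, a patient has been randomised to one treatment but received the other one at inclusion (forced allocation". It adds that this patient stayed on the treatment received at the later dispensations. SAP 4.3.1 no longer refers to the initially randomised treatments when it states the primary estimand.

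SAP 4.3.3 keeps treatment-policy estimands for ESSDAI and ESSPRI in the Randomised Set. Its data rule is "All observed values will be used regardless of occurrence of an IE", and its main analysis is the primary model. It gives no arm definition of its own, so SAP 2.2 applies.

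**The concern.** The primary estimand asks what the drug does in patients who take it without intercurrent events. For that question, placing a patient who took one treatment throughout with the others who took it can be argued.

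Treatment policy is where the plan sets intercurrent events aside and uses all observed data. A reader would expect at least that analysis to compare the arms as allocated, which is also the protocol's general rule for efficacy. Under the SAP it does not. The sensitivity analysis in SAP 4.3.1.2 changes only the imputation, and the other estimands inherit SAP 2.2.

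At stake is whether the report contains any efficacy estimate in the arms that randomisation formed, and how far one reassigned patient in a trial planned at 30 and 15 could move the treatment-policy estimate.

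**Working it through.** **Inputs.** From SAP 1.2 (identical in protocol 10.2): 30 patients on S95011, 15 on placebo, SD 6, and a success rule that requires one-sided significance at 10% and an estimated difference of at least 3 points. From SAP 6: one patient whose W000 treatment differed from the randomised one. Assumed: a true effect of 4 points (the value at which the plan quotes about 70%), unadjusted means, and a patient otherwise typical of those enrolled. The direction of the error is not given, so both are shown. Benefit is counted as positive.

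**1. The plan's own figure.**
- SE = 6 × √(1/30 + 1/15) = 1.90.
- Significance needs about 1.2816 × 1.897 = 2.43 points, so the 3-point criterion binds.
- Chance of success at a true 4 points: Φ((4 − 3)/1.897) = 70.1%. At a true 3 points: 50.0%.
- The plan states about 70% and about 50%, so its figures reproduce.

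**2. Expected difference between the groupings.** Grouped as received, every patient is counted under the drug taken and the expected estimate is 4.00.
- Randomised to S95011, given placebo: as randomised, 4 × 29/30 = 3.87; difference 4/30 = 0.13.
- Randomised to placebo, given S95011: as randomised, 4 × 14/15 = 3.73; difference 4/15 = 0.27.
- With a true effect of 0, both differences are 0.

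**3. Difference in a single trial.** Moving one patient changes both arm means, so the shift varies around its expectation.
- S95011 to placebo: SD = 6 × √[(1/30 + 1/16)² + (1/30)²/29 + (1/16)²/15] = 0.58.
- Placebo to S95011: SD = 6 × √[(1/31 + 1/15)² + (1/31)²/30 + (1/15)²/14] = 0.60.
- A simulation of 200,000 trials at a 4-point effect gave mean shifts of 0.131 and 0.268, the same SDs, and 95% ranges of −1.02 to 1.28 and −0.92 to 1.45 points.
- With an outcome SD of 4, the low end of the range the plan cites, the SDs are 0.39 and 0.40.

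**4. On the scale of the success rule.** Grouped as randomised, the chance at a true 4 points would be Φ((3.87 − 3)/1.897) = 67.6% or Φ((3.73 − 3)/1.897) = 65.0%, against 70.1% in step 1. The plan does not apply this rule to treatment policy, so these figures bear only on an as-randomised display of the primary analysis.

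**The case against.** The strongest defence is that the change is open and reasoned, concerns one patient, and was triggered at W000, before any post-baseline outcome. That patient took the other treatment throughout. Treatment policy in the plan sets aside a listed set of intercurrent events, and wrong allocation at W000 is not on the list, so SAP 4.3.3 does not contradict itself. The calculation above also ignores the planned adjustment for baseline and strata. And an SD of about 0.6 is the ordinary leverage of one patient in a small trial; it does not show which grouping is right. All of this stands, and it limits the weight of the point. It does not remove the departure from protocol 10.1.1.2 or supply an as-randomised efficacy analysis.

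Two stronger readings are tempting, and the documents do not support them:
- A reader might infer that the SAP treats like errors unequally, because a wrong unit after W000 leaves the patient in the starting arm while a wrong treatment at W000 moves the patient. SAP 2.2 applies one first-received rule to both: after a later switch, "the patient will be considered in the treatment group corresponding to their TU(s) received until the switch". The cases also differ. One patient took the other treatment from the start; the other only potentially switched later.
- A reader might infer that regrouping this patient would make the result rest on randomisation alone. It would not. SAP 2.1 and 6 also limit the Randomised Set to included patients, which drops one patient randomised by mistake.

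**Conclusion.** The point holds and is minor. Every planned efficacy analysis, including treatment policy, groups patients by treatment received at W000, and the protocol's as-randomised grouping survives nowhere.

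A reader might go further and conclude that the randomised comparison is lost or the result biased towards the drug. The documents do not support that: they describe one such patient, whose regrouping is declared, and with no drug effect the expected shift is 0 if the forced allocation was unrelated to prognosis. With a 4-point effect the expected shift is 0.13 or 0.27 points, about 7% or 14% of the 1.90 standard error (0.13/1.90 and 0.27/1.90). A realised shift of about 0.6 points would be unremarkable. These sizes rest on the planned 30/15 split, SD 6 and unadjusted means. The success criteria rest on the primary estimand, where grouping by treatment received is arguable.

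**What to change.** In SAP 4.3.3, define the arms for the ESSDAI and ESSPRI treatment-policy estimands by randomised treatment, as in protocol 10.1.1.2, for both the main and the responder analyses. Because imputation is done separately by arm, use the randomised arm in the imputation model as well as the analysis model. Keep treatment received for safety. Optionally, show the primary analysis as randomised as a sensitivity analysis. State alongside these results that the Randomised Set still excludes the patient randomised by mistake but not included.

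The cost is a few lines of SAP text and a rerun with the existing model; no new data are needed. The downside is a small expected dilution, 0.13 or 0.27 points at a 4-point effect, because one patient is counted in an arm whose treatment they did not receive.
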